### **3. PARTICIPANT SELECTION AND ENROLLMENT PROCEDURES**

#### **3.1 Inclusion Criteria**

- Biopsy proven prostate adenocarcinoma
- Rising PSA after definitive therapy with prostatectomy or radiation therapy (external beam or brachytherapy)
  - a. Post radical prostatectomy (RP) – AUA recommendation (39)
    - i. PSA greater than 0.2 ng/mL measured after at least 6 weeks from radical prostatectomy
    - ii. Confirmatory persistent PSA greater than 0.2 ng/mL (total of two PSA measurements greater than 0.2 ng/mL)
  - b. Post-radiation therapy –ASTRO-Phoenix consensus definition (40)
    - i. A rise of PSA measurement of 2 or more ng/mL over the nadir
- Able to provide written consent
- Karnofsky performance status of  $\geq 50$  (or ECOG/WHO equivalent)

#### **3.2 Exclusion Criteria**

- Less than 18 years old at the time of radiotracer administration
- Inability to lie still for the entire imaging time
- Inability to complete the needed investigational and standard-of-care imaging examinations due to other reasons (severe claustrophobia, radiation phobia, etc.)
- Any additional medical condition, serious intercurrent illness, or other extenuating circumstance that, in the opinion of the Investigator, may significantly interfere with study compliance
- Known allergy, hypersensitivity, or intolerance to the investigational product or its excipients
- Metallic implants (contraindicated for MRI)

#### **3.3 Informed Consent Process**

All participants will be provided a consent form describing the study with sufficient information for participants to make an informed decision regarding their participation. Participants must sign the IRB approved informed consent prior to participation in any study specific procedure. The participant must receive a copy of the signed and dated consent document. The original signed copy of the consent document must be retained in the medical record or research file.

#### **3.4 Study Timeline**

##### **3.4.1 Primary Completion:**

The study will reach primary completion (all 50 participants enrolled) 24 months from the time the study opens to accrual.

##### **3.4.2 Study Completion:**

The protocol will reach study completion when all participants will have 12 months of clinical follow-up completed.

## 4. IMAGING AGENT INFORMATION

### 4.1 Study Agent

We will use  $^{68}\text{Ga}$ -NeoBOMB1 and  $^{68}\text{Ga}$ -PSMA R2 as the PET radiopharmaceuticals. These will be provided as ready-to-inject unit doses from a commercial radiopharmacy (Sofie Biosciences, previously dba Zevacor). No manufacturing will take place at Stanford University.

The administered dosage of  $^{68}\text{Ga}$ -NeoBOMB1 is 150 to 250 MBq IV. The *in vivo* distribution of  $^{68}\text{Ga}$ -NeoBOMB1 was studied by Dalm et al in Balb c nu/nu mice bearing the PC-3 tumor-xenograft, injected with  $\sim 13$  MBq/250 pmol  $^{68}\text{Ga}$ -NeoBOMB1 (specific activity  $\sim 50$  MBq/nmol) (41). At 6 time-points (15 min; 30 min; 60 min; 2 h; 4 h; and 6 h) post-injection (p.i.), tumor and organ uptake was determined using a gamma counter. To assess receptor-specificity additional groups of animals were co-injected with an excess of unlabelled NeoBOMB1 (40 nmol). Results of the biodistribution studies were also used to determine pharmacokinetics parameters and to perform dosimetry calculations. The highest tumor uptake of  $12.4 \pm 2.3$  %ID/g tissue was measured at 2 h p.i. At that time point, the uptake in the pancreas was  $22.7 \pm 3.3$  %ID/g tissue. Uptake values in kidney and liver were  $5.7 \pm 2.4$  and  $8.3 \pm 1.8$  % ID/g tissue, respectively, indicating renal and hepatobiliary excretion. When receptors were blocked by co-injection with an excess of unlabelled NeoBOMB1, uptake in GRPR-expressing tissues decreased, as observed in tumor and pancreas, where relative uptake reached  $1.0 \pm 0.1$  and  $0.7 \pm 0.1$  %ID/g tissue, respectively. Pharmacokinetic calculations resulted in a tumor clearance half-life of  $6.9 \pm 2.8$  h and a pancreas clearance half-life of  $12.9 \pm 4.0$  h. Clearance from blood proceeded according to a bi-phasic pattern:  $66 \pm 9$  % with half-life of  $8 \pm 5$  min and 34% with half-life of  $50 \pm 15$  min.

Using the OLINDA/EXM for  $^{68}\text{Ga}$  and assuming equal uptake per organ in human and mice, extrapolation to humans was performed obtaining an effective dose of 0.039 mSv/MBq. Estimated absorbed doses extrapolated from animal study showed that the critical organ is the pancreas (0.341 mGy/MBq). However, it is important to note that the contribution to the effective dose (calculated using the ICRP-60 weighting factors) for this organ is 0.002 mSv/MBq. Therefore, with an administered dose of 250 MBq (max dose), the resulting expected dose in the pancreas will be 0.43 mSv (50 mSv is the organ radiation dose limit for adults receiving a single administration, as per the Guidance for Industry and Researchers; “The Radioactive Drug Research Committee: Human Research Without an Investigational New Drug Application”, August 2010).

The estimated effective dose for total human body, for an injected dose of 150 to 250 MBq is between 5.85 to 9.75 mSv, which is below the FDA limit of 30 mSv for adult research subjects receiving a single dose (Guidance for Industry and Researchers; “The Radioactive Drug Research Committee: Human Research Without an Investigational New Drug Application”, August 2010).

**Table 1: Absorbed dose estimates for  $^{68}\text{Ga}$ -NeoBOMB1 in humans (mGy/MBq). Effective dose and contributions to the effective (ED Cont.) are also reported (mSv/MBq).**

Target Organ	Beta	Photon	Total	ED Cont.
Adrenals	2.03E-03	6.43E-03	8.46E-03	4.23E-05
Brain	2.03E-03	1.27E-03	3.30E-03	1.65E-05
Breast	2.03E-03	1.64E-03	3.66E-03	1.83E-04
Gallbladder Wall	2.03E-03	9.28E-03	1.13E-02	0.00E+00
LLI Wall	1.45E-02	8.13E-03	2.27E-02	2.72E-03
Small Intestine	7.44E-03	6.08E-03	1.35E-02	6.76E-05
Stomach Wall	9.23E-03	5.83E-03	1.51E-02	1.81E-03
ULI Wall	3.17E-02	7.53E-03	3.92E-02	1.96E-04
Heart Wall	2.03E-03	3.57E-03	5.59E-03	0.00E+00
Kidneys	3.19E-02	7.37E-03	3.93E-02	1.96E-04
Liver	6.10E-02	1.48E-02	7.58E-02	3.79E-03
Lungs	2.05E-03	2.64E-03	4.69E-03	5.63E-04
Muscle	2.29E-05	3.25E-03	3.28E-03	1.64E-05
Ovaries	2.03E-03	7.80E-03	9.82E-03	1.96E-03
Pancreas	3.15E-01	2.65E-02	3.41E-01	1.71E-03
Red Marrow	1.41E-03	3.34E-03	4.75E-03	5.70E-04
Osteogenic cells	3.15E-03	2.61E-03	5.76E-03	5.76E-05
Skin	2.03E-03	1.59E-03	3.62E-03	3.62E-05
Spleen	5.24E-03	4.94E-03	1.02E-02	5.09E-05
Testes	2.03E-03	4.77E-03	6.80E-03	0.00E+00
Thymus	2.03E-03	1.68E-03	3.70E-03	1.85E-05
Thyroid	2.03E-03	1.18E-03	3.21E-03	1.61E-04
Urinary Bladder Wall	4.29E-01	5.88E-02	4.88E-01	2.44E-02
Uterus	2.03E-03	1.42E-02	1.62E-02	8.10E-05
Total Body	4.67E-03	3.45E-03	8.12E-03	0.00E+00
Effective Dose			3.86E-02	

The administered dosage of  $^{68}\text{Ga}$ -PSMA R2 is 150 to 250 MBq IV. The effective dose is expected to be similar to that from  $^{68}\text{Ga}$ -PSMA-617.

Within healthy organs, the kidneys and salivary glands showed the highest  $^{68}\text{Ga}$ -PSMA-617 uptake. The average radiation exposure (effective dose) was approximately 0.021 mSv/MBq.

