## **2.2 Study Agent**

We will use Ga-NeoBOMB1 and Ga-PSMA R2 as the PET radiopharmaceuticals. These are not FDA-approved products, but we have letters of cross-reference for FDA-approved INDs allowing the use of these tracers in this proposed clinical indication under a Stanford investigator sponsored IND (████████).

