## 8. ADVERSE EVENTS AND REPORTING PROCEDURES

### 8.1 Potential Adverse Events

The administration of the radioactive substance will feel like a slight pinprick when given by IV injection. Patients who are claustrophobic may feel some anxiety while positioned in the scanner. Also, some patients find it uncomfortable to hold one position for more than a few minutes. Because the radioactivity is very short-lived, the expected radiation exposure of the whole body and critical organs is low. The substance amount (PSMA R2 and NeoBOMB1) is so small that it does not affect the physiological processes of the body.

This research study involves exposure to radiation from one Ga-NeoBOMB1 PET/MRI. There is no radiation exposure from MRI. The estimated effective dose for total human body, for an injected dose of 150 to 250 MBq is between 5.85 to 9.75 mSv, approximately equal to 11.7 to 19.5% of the limit that radiation workers (for example, a hospital X-ray technician) can receive in one year.

This research study also involves exposure to radiation from one Ga-PSMA-R2 PET/MRI. There is no radiation exposure from MRI. The effective dose from Ga-PSMA-R2 PET is similar to Ga-PSMA-11 or Ga-PSMA-617. The estimated effective dose for total human body, for an injected dose of 150 to 250 MBq, is between 3.15 to 5.25 mSv, approximately equal to 6.3-10.5% of the limit that radiation workers (for example, a hospital X-ray technician) can receive in one year.

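### Section 4.1 compares the pancreas's weighted share of effective dose (0.43 mSv) with a 50 mSv organ limit; Table 1 implies 51 to 85 mGy to pancreas and 73 to 122 mGy to bladder wall

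*Combined protocol and SAP*

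**What the plan says.** Section 4.1 states that the administered activity of 68Ga-"NeoBOMB1 is 150 to 250 MBq IV". It reports dosimetry scaled from mice to humans, "assuming equal uptake per organ in human and mice", and makes three statements in sequence:

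- On absorbed dose, "the critical organ is the pancreas (0.341 mGy/MBq").
- The "contribution to the effective dose (calculated using the ICRP-60 weighting factors) for this organ is 0.002 mSv/MBq".
- It then infers that, at the 250 MBq maximum, "the resulting expected dose in the pancreas will be 0.43 mSv (50 mSv is the organ radiation dose limit for adults" given one administration. The limit is attributed to guidance on human research without an IND.

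Table 1, in the same section, lists for each organ a total absorbed dose (mGy/MBq) and a contribution to effective dose (mSv/MBq). Pancreas has 3.41E-01 and 1.71E-03. The row "Urinary Bladder Wall" has 4.88E-01 and 2.44E-02.

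Section 2.2 places the study "under a Stanford investigator sponsored IND". Section 8.1 tells the reader: "Because the radioactivity is very short-lived, the expected radiation exposure of the whole body and critical organs is low".

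**The concern.** The figure compared with the organ limit appears to be the wrong quantity. A contribution to effective dose is the organ's dose after multiplication by a small tissue weight, so that organs can be added into one whole-body number. It does not measure what the organ receives and cannot be held against an organ limit. The text also calls the pancreas the critical organ although Table 1 shows a higher value for bladder wall.

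This is the only organ-level safety comparison in the available text for this tracer. As written, it shows a margin of more than 100-fold (50/0.43 = 116). If the like-for-like value lies above 50, a reader who relies on the narrative takes away the opposite of what the table supports, and is directed to the organ with the second-highest dose.

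**Working it through.** **Inputs, all from section 4.1 and its Table 1.** Activity 150 to 250 MBq. Pancreas: absorbed dose 0.341 mGy/MBq, contribution to effective dose 0.00171 mSv/MBq. Bladder wall: 0.488 mGy/MBq and 0.0244 mSv/MBq. Liver (next highest): 0.0758 mGy/MBq. Organ limit as the protocol quotes it: 50 mSv.

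**Step 1. Reproduce the stated figure.** Contribution to effective dose × activity: 0.00171 × 250 = 0.4275, which rounds to 0.43 mSv. The rounded coefficient in the text would give 0.002 × 250 = 0.50, so the unrounded table entry was used. The multiplication is right.

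**Step 2. Identify the quantity.** The implied tissue weight is 0.00171/0.341 = 0.005 for pancreas and 0.0244/0.488 = 0.05 for bladder wall. The whole contribution column sums to 0.03865 mSv/MBq, matching the printed effective dose of 3.86E-02. The column is therefore the tissue-weighted one, and 0.43 mSv is the pancreas's share of the whole-body figure.

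**Step 3. Compute organ dose.** Organ dose = absorbed-dose coefficient × activity.

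| Organ | 150 MBq | 250 MBq | Activity giving 50 mGy |
|---|---|---|---|
| Pancreas | 0.341 × 150 = 51.2 mGy | 0.341 × 250 = 85.3 mGy | 50/0.341 = 147 MBq |
| Bladder wall | 0.488 × 150 = 73.2 mGy | 0.488 × 250 = 122.0 mGy | 50/0.488 = 102 MBq |
| Liver | 0.0758 × 150 = 11.4 mGy | 0.0758 × 250 = 19.0 mGy | not reached at planned activity |

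The understatement for pancreas at 250 MBq is 85.25/0.4275 = 199-fold, the inverse of the 0.005 weight.

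**Step 4. Compare with 50 mSv.** Setting mGy against mSv requires a radiation weighting factor, which the documents do not state. With a factor of 1 for beta and photon radiation, pancreas and bladder wall lie above 50 over the whole planned range. Pancreas is only 2% above at 150 MBq (51.15/50 = 1.023).

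**Step 5. Check without the limit.** If 0.43 were the pancreas dose at 250 MBq, the supposed critical organ would receive less than every organ in the table. The lowest, thyroid, gets 0.00321 × 250 = 0.80 mGy, and the total-body value is 0.00812 × 250 = 2.03 mGy. So the stated figure contradicts Table 1 whichever benchmark is used (again taking mGy and mSv as numerically equal).

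**Step 6. Critical organ.** Bladder wall exceeds pancreas by 0.488/0.341 = 1.43, or 43% per MBq. It is the highest entry in both columns.

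**Step 7. What is unaffected.** Whole-body effective dose: 0.039 × 150 = 5.85 and 0.039 × 250 = 9.75 mSv, as stated.

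**The case against.** The strongest reply concedes the mismatch and disputes its weight.

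- **The benchmark does not clearly apply.** It comes from guidance for research without an IND, and this study has one. This stands: no breach of a binding rule is shown. But the protocol chose the benchmark, and the reassurance it draws from the comparison does not hold.
- **Nothing in the trial depends on 0.43 mSv.** No eligibility rule, activity, endpoint or stopping rule in the available text uses it. This also stands. The matter is a wrong participant-safety statement, not a flaw in design or analysis.
- **The right coefficients are printed.** A dosimetry specialist could find the slip within the section. That limits the harm, but the stated conclusion still contradicts the table.
- **The reversal is fragile for pancreas at the low end.** It is 2% above 50 at 150 MBq, with coefficients extrapolated from mice whose pancreas uptake at 2 h is given as 22.7 ± 3.3 %ID/g, a spread of about 15%. This is fair for pancreas near 150 MBq. It has less force at 250 MBq and for bladder wall, which is well above 50 throughout. The extrapolation cannot rescue 0.43, which comes from the same data.
- **Section 8.1 stands on its own.** Its reason is the short life of the radioactivity, its numbers are effective doses, and it cites no organ limit. This largely stands. Its description of critical-organ exposure as low sits badly with Table 1 only if the 50 mSv of section 4.1 is carried over, so revising it is secondary.

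**Conclusion.** The concern holds. Section 4.1 labels a tissue-weighted contribution as an organ dose and compares it with an organ limit. At 250 MBq the stated pancreas value is about 200 times too low (0.43 against 85.3), and the comparison reverses when like is compared with like. Bladder wall, not pancreas, has the highest absorbed dose.

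The discrepancy within the protocol follows from its own table. The reversal against 50 mSv rests on a radiation weighting factor of 1, on the limit as the protocol quotes it, and on mouse-derived coefficients that human data may change. It is secure for bladder wall on the printed coefficients and marginal for pancreas near 150 MBq. The result is a comparison that fails on the protocol's own terms, not evidence that the planned activity is unacceptable.

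**What to change.** In section 4.1:

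1. Replace the 0.43 mSv sentence with the absorbed doses over 150 to 250 MBq: pancreas 51.2 to 85.3 mGy and bladder wall 73.2 to 122.0 mGy. Compare both with the cited 50 mSv on one scale, stating the radiation weighting factor.
2. Name bladder wall as the organ with the highest absorbed dose, followed by pancreas.
3. Repeat beside these figures that they are extrapolated from mice, and say why guidance for research without an IND is the benchmark for a study under an IND.
4. Have radiation safety re-check the comparison before the amendment is issued.

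Secondarily, reword the description of critical-organ exposure in section 8.1 so that it fits the corrected figures.

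The cost is amendment wording and one radiation-safety re-check. The stated safety margin becomes less favourable. No change to activity, design or sample size is proposed.

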## 2.5 Study Design

This is a prospective, single center, single-arm phase II study enrolling 50 participants with biochemically recurrent prostate cancer. All patients will first be seen by a Stanford Cancer Institute physician and then referred if appropriate on clinical grounds to [name] or his colleagues for this study. Eligible participants will undergo baseline assessments at enrollment. The following steps will take place after the participant has signed the written consent (participants will be randomized to have  $^{68}\text{Ga}$ -NeoBOMB1 first followed by  $^{68}\text{Ga}$ -PSMA R2 within 2 weeks or  $^{68}\text{Ga}$ -PSMA R2 first followed by  $^{68}\text{Ga}$ -NeoBOMB1 within 2 weeks [50/50 chance for each schedule]).

1. Participant will be asked to drink 1 to 2 glasses of water before arrival at the clinic
2. Participants will be weighed and vital signs (heart rate, blood pressure, respiratory rate, pulse oxymetry) will be recorded
3. Participant will be injected IV with 150 to 250 MBq of  $^{68}\text{Ga}$ -NeoBOMB1
4. Vital signs (heart rate, blood pressure, respiratory rate, pulse oxymetry) will be recorded after the injection
5. Participant will void immediately prior to the scan
6. Approximately 45 minutes after the radiopharmaceutical IV administration, data acquisition will begin in the pelvic region and move toward the head. First, localizer MRI scans will be performed to define the table positions. After correct positioning of the spatial acquisition windows is ensured, the combined PET/MRI acquisition will be initiated with 3 to 5 table positions at a 4-min acquisition time per table position.
7. Participants will be given a copy of the consent form s/he signed and will be dismissed.
8. Vital signs (heart rate, blood pressure, respiratory rate, pulse oxymetry) will be recorded again at the completion of the study
9. Participants will be contacted at 24 to 72 hours following the scan in order to capture potential occurring Adverse Events.

The same will be repeated for  $^{68}\text{Ga}$ -PSMA R2 (within 2 weeks of  $^{68}\text{Ga}$ -NeoBOMB1):

1. Participant will be asked to drink 1 to 2 glasses of water before arrival at the clinic
2. Participants will be weighed and vital signs (heart rate, blood pressure, respiratory rate, pulse oxymetry) will be recorded
3. Participant will be injected IV with 150 to 250 MBq of  $^{68}\text{Ga}$ -PSMA R2

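### Section 4.1 reports a tissue-weighted contribution to effective dose (0.43 mSv) as the NeoBOMB1 pancreas dose; Table 1 gives 51 to 85 mGy for the pancreas and 73 to 122 mGy for the bladder wall

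*Combined protocol and SAP*

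**What the plan says.** Section 4.1 extrapolates mouse biodistribution data to humans, "assuming equal uptake per organ in human and mice", and draws three statements about the pancreas from the result.

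- Organ dose: "Estimated absorbed doses extrapolated from animal study showed that the critical organ is the pancreas (0.341 mGy/MBq").
- Weighted contribution: "the contribution to the effective dose (calculated using the ICRP-60 weighting factors) for this organ is 0.002 mSv/MBq".
- Conclusion at 250 MBq: "the resulting expected dose in the pancreas will be 0.43 mSv (50 mSv is the organ radiation dose limit for adults" given a single administration, citing guidance on human research without an IND).

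Table 1 lists, for each organ, the absorbed dose in mGy/MBq (*Total*) and, in a separate column, the contribution to effective dose in mSv/MBq (*ED Cont.*). The row with the highest absorbed dose is "Urinary Bladder Wall", at 4.88E-01 mGy/MBq. The text around the table does not mention it.

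Section 2.2 says the tracers are used "in this proposed clinical indication under a Stanford investigator sponsored IND". Section 8.1 says, giving the short life of the radioactivity as its reason, that "the expected radiation exposure of the whole body and critical organs is low".

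**The concern.** An organ dose limit applies to the dose received by the organ. A contribution to effective dose is that organ dose multiplied by a tissue weighting factor, so that it can be summed with other organs into a whole-body figure. For the pancreas the weight is very small, and the product says almost nothing about what the pancreas receives. Section 4.1 describes the quantity correctly in one sentence. In the next it calls the same quantity, multiplied by 250 MBq, the dose in the pancreas and sets it against an organ limit.

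In the text available, this is the only comparison of an organ dose with a limit; the other comparisons use effective dose. As written it appears to pass by a factor of more than 100 (50/0.43 = 116). A radiation-safety or ethics reviewer who relies on that sentence is reassured by a number that does not measure what it claims to. The organ with the highest tabulated dose is not assessed at all, and nothing valid in 4.1 supports calling critical-organ exposure low for these two organs.

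**Working it through.** **Inputs.** Activity 150 to 250 MBq (sections 2.5 and 4.1). From Table 1: pancreas *Total* 0.341 mGy/MBq and *ED Cont.* 1.71E-03 mSv/MBq; bladder wall *Total* 0.488 mGy/MBq and *ED Cont.* 2.44E-02 mSv/MBq; liver *Total* 0.0758 mGy/MBq; effective dose 3.86E-02 mSv/MBq. One assumption the protocol does not state: 1 mGy = 1 mSv, as is standard for beta and photon radiation.

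**Reproducing the stated figure.** 1.71E-03 x 250 = 0.4275, which rounds to 0.43 mSv. The rounded 0.002 in the text would give 0.50, so the unrounded *ED Cont.* entry was used. The implied tissue weight is 1.71E-03 / 0.341 = 0.005.

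**Organ dose = activity x *Total*.**

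| Organ | 150 MBq | 200 MBq | 250 MBq | Activity reaching 50 mSv |
|---|---|---|---|---|
| Pancreas (0.341) | 51.2 | 68.2 | 85.3 | 50/0.341 = 146.6 MBq |
| Bladder wall (0.488) | 73.2 | 97.6 | 122.0 | 50/0.488 = 102.5 MBq |

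Both crossing points lie below the 150 MBq minimum. The next highest organ, the liver, reaches 0.0758 x 250 = 19.0, so the problem is limited to these two organs.

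**Size of the discrepancy.** 85.25 / 0.4275 = 199, the inverse of the 0.005 tissue weight. The whole gap is therefore explained by use of the weighted column.

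**Tolerance for extrapolation error.** The fraction of the tabulated value at which the organ would be at exactly 50 is:

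- at 250 MBq: pancreas 50/85.25 = 59%, bladder wall 50/122.0 = 41%;
- at 150 MBq: pancreas 50/51.15 = 98%, bladder wall 50/73.2 = 68%.

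**Share of effective dose.** Bladder wall 2.44E-02 / 3.86E-02 = 63%; pancreas 1.71E-03 / 3.86E-02 = 4.4%.

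**What is not affected.** The *ED Cont.* column sums to 0.0386, matching the printed total. The whole-body range also reproduces: 0.039 x 150 = 5.85 mSv and 0.039 x 250 = 9.75 mSv.

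**The case against.** The strongest reply is that nothing is hidden. The absorbed dose coefficient stands two sentences before the 0.43, the weighted quantity is correctly named once, and Table 1 separates the two columns, so a dosimetry reader can recover the organ dose in one multiplication. That is true, but the conclusion given to the reader is still 0.43 against 50, and that conclusion is wrong.

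The 50 mSv figure may not govern this trial, since it comes from guidance for research without an IND. This stands, and it is why no breach can be claimed. The protocol nevertheless chose this benchmark, and if it does not apply, it should not be there.

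The doses are mouse extrapolations. This also stands, and it matters most for the pancreas at 150 MBq, where 51.15 is only 2.3% above 50 while mouse pancreas uptake in section 4.1 is 22.7 ± 3.3 %ID/g, about ±15%. The low end cannot be told apart from the benchmark. But 0.43 comes from the same extrapolation, so this uncertainty cannot explain a 200-fold gap.

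The bladder value depends on voiding. Section 2.5 asks participants to drink water beforehand, and "Participant will void immediately prior to the scan". No voiding model is given for Table 1, so the human bladder dose could be lower than tabulated. The pancreas dose would not change.

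Finally, section 8.1 does not cite 0.43, and the effective doses it gives are correct. That is so, and the link to 8.1 is correspondingly weaker.

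**Conclusion.** The concern holds. Section 4.1 labels a tissue-weighted contribution as the pancreas dose and compares it with an organ limit; at 250 MBq the stated figure is about 200 times too small. On the protocol's own table the pancreas receives 51.2 to 85.3 mSv and the bladder wall 73.2 to 122.0 mSv over the permitted range. The pancreas is therefore not the highest-dose organ, and the quoted benchmark is not met for either organ at any permitted activity.

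This rests on Table 1 as printed and on 1 mGy = 1 mSv. It describes the protocol's estimates, not measured human doses, and does not establish that any limit binding on this trial is exceeded. Nor does it show that the activity range was chosen because of the 0.43 figure or that the range must change. The error should be corrected because it is the organ-dose assurance offered for the administered activity.

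**What to change.** In section 4.1:

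- replace 0.43 mSv with the unweighted organ doses over 150 to 250 MBq (pancreas 51.2 to 85.3 mSv, bladder wall 73.2 to 122.0 mSv), marked as mouse extrapolations;
- state the bladder-voiding assumption behind Table 1;
- name the bladder wall as the highest-dose organ in that table;
- state whether the 50 mSv limit applies under the IND and, if it does not, remove it or name the criterion that does.

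In section 8.1, replace the unqualified statement that critical-organ exposure is low with these ranges.

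Optionally, give the kidney dose for the PSMA-617 proxy from Table 3: mean (0.239 + 0.085 + 0.305 + 0.196)/4 = 0.206 mGy/MBq, or 30.9 to 51.6 mSv over 150 to 250 MBq, from four patients. Note that the protocol claims similarity to PSMA R2 only for effective dose. The correction above does not depend on this addition.

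The cost is a text change in 4.1 and one sentence in 8.1, submitted as an IRB modification. The stated safety figures become less favourable, and a radiation-safety reviewer may ask for a justification of the activity range. Endpoints, analysis and sample size are unaffected.
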